8.4.2 Secondary Safety Endpoint Analysis

The secondary safety analysis of combined minor venous access site closure related complications within 30 days post-procedure, attributed directly to VCD or manual compression without other likely cause will be summarized on a per-limb basis. The proportion of limbs experiencing a minor closure related complication will be calculated for each treatment group along with 95% confidence intervals. The difference between the proportions will then be estimated along with a 95% confidence interval.

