16.9.2 Secondary Safety Analysis

The secondary safety analysis of combined minor venous access site closure related complications within 30 days post-procedure, attributed directly to VCD or manual compression without other likely cause will be summarized on a per-limb basis. The proportion of limbs experiencing a minor closure related complication will be calculated for each treatment group along with 95% confidence intervals. The difference between the proportions will then be estimated along with a 95% confidence interval.

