16.9.3 Secondary Efficacy Analyses

Time to Discharge Eligibility, defined as the elapsed time between removal of the final MYNX CONTROL[™] Venous VCD (device group) or removal of the final sheath (control group), and when the subject is eligible for discharge from the institution (in hours) will be summarized on a perpatient basis.

Time to discharge eligibility is a powered secondary endpoint. The average time to discharge eligibility will be compared between the device and control groups at the 0.025 level of significance. The specific hypotheses being tested are:

Ho: $\mu_{Mynx \ Control} \geq \mu_{manual \ compression}$

Ha: $\mu_{Mynx \ Control} < \mu_{manual \ compression}$

where μ_x is the average time to discharge eligibility for the specified group. A p-value for this one-sided test less than 0.025 will indicate that the time to discharge eligibility for the subjects using the MYNX CONTROLTM Venous Vascular Closure Device (VCD) was significantly less than for those where manual compression was used. The standard two group T-test will be used to make this comparison.

The difference between treatment groups in average time to discharge will also be estimated with 95% confidence intervals calculated using the T-distribution.

The following secondary endpoints are considered ad hoc analyses and are not powered.

Procedural Success defined as the attainment of final hemostasis at all venous access sites without major venous access site closure-related complications through 30 days will be summarized on a per access site basis and on a per-limb basis. Procedural success will be estimated for each treatment group separately with 95% confidence intervals followed by an

Version: 3.0 / 31Jan2023

estimate of the difference in procedural success between the treatment groups and a 95% confidence interval on the difference.

Device Success defined as the ability to deploy the VCD delivery system, deliver the polyethylene glycol hydrogel sealant, and achieve hemostasis will be summarized on a per access site basis for the device group only. The proportion of device successes will be estimated along with a 95% confidence interval.

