5 SAMPLE SIZE

All sample sizes were calculated assuming a 2:1 ratio of MYNX CONTROL[™] VCD to manual compression.

Time to Ambulation:

Time to ambulation is a co-primary endpoint for effectiveness. The Type 1 error for this calculation was set at 0.025 for a one-sided test. Assuming that the treatment group ambulates in 3.0 hours on average and the control group ambulates in 6.0 hours and both groups have a standard deviation of 6.0 hours, then an effective sample size of 192 subjects provides 90% power to detect this difference in time to ambulation between the two groups of subjects. Adjusting for a missing data rate of 5%, total enrollment is 204 subjects.

Time to Hemostasis:

Time to hemostasis is a co-primary endpoint for effectiveness. The Type 1 error for this calculation was set at 0.025 for a one-sided test. A generalized linear mixed model will be used to compare the MYNX CONTROL[™] Venous VCD device with manual

compression (control). Initial estimates of the average time to hemostasis were taken from historical MYNX family devices and compared to manual compression. Previous MYNX family studies only studied one access site per subject within the femoral artery. The observed average time to hemostasis as well as the standard deviations of those measurements helped inform the design of this trial where the standard deviation would be used as an estimate of subject-to-subject variation. For the sample size calculation, it is assumed that each subject has 3 access sites in the femoral vein. These access sites will be closed with either the MYNX CONTROL[™] Venous VCD device or manual compression. Only one method of closure will be used per subject. Time to hemostasis will be measured for each access site separately.

It is assumed that hemostasis times are log-normally distributed. Using previous study data where time to hemostasis averaged 6 minutes for the MYNX CONTROLTM Venous VCD device and 13 minutes for manual compression, estimates of μ and σ of the lognormal distribution were obtained and used in the calculation of sample size for this endpoint.

A generalized linear mixed model is used with the subject as a random effect. The specific model used is:

$$y_{ijk} = \mu + \tau_i + S_{j(i)} + e_{k(ij)}$$

where τ_i is the treatment effect and S_{ij} is the random effect of subject within treatment. e_{ijk} is the unexplained variation in the model. Further, it is assumed that:

$$y_{ijk} \sim N(\mu_{ij}, \sigma^2)$$

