 $S_{j(i)} \sim N(0, \sigma_S^2)$

and

 $e_{k(ij)} \sim N(0, \sigma_e^2)$

To adjust for the correlation in hemostasis time between the access sites within subject it is assumed that the correlation structure is compound symmetric. A sample size of 150 subjects (100 MYNX CONTROL[™] VCD and 50 manual compression) will provide approximately 95% power to detect a difference in hemostasis times of 7 minutes between MYNX CONTROL[™] VCD and manual compression. Note that these calculations were made in the log transformed space to assess power. Also, the variation between access sites within subject was estimated at approximately half of the variation observed between subjects.

Major Complication Rate:

The rate of combined major venous access site closure-related complications through 30 days post procedure, attributed directly to VCD or manual compression without other likely cause is the primary safety endpoint. The one-sided Type I error was set to 0.025 for the purpose of sample size calculation. The safety endpoint will be analyzed using a non-inferiority approach on a per limb basis. For the purposes of sample size

calculation, both groups are assumed to have a 1.5% major complication rate. The non-inferiority window has been established at 5 percentage points.

Within-subject correlation can affect the power of the study depending on the degree of correlation. However, the degree of correlation within-subject due to potentially multiple limbs is unknown and there is not robust and relevant data on which to base any associated assumption. Since this is unknown, conservatively sample size is calculated assuming only one limb per subject, or in other words, the number of subjects in the study assuming independence between subjects. Calculations for a two-sample test of binomial proportions for a Z test under a normal approximation show a sample size of 204 subjects should provide approximately 80% power for this endpoint. To the extent that some subjects will contribute multiple limbs to the actual analysis, the power would be higher than that from calculations based only on the numbers of independent subjects. Though missing data for the primary safety endpoint is unlikely, the additional data contributed by multiple limbs will help offset any power loss due to missing data.

Time to Discharge Eligibility (secondary endpoint):

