8 STATISTICAL METHODS OF ANALYSIS

8.1 General Considerations

All statistical programming will be performed using SAS[®] version 9.4 or above, or other widely accepted statistical or graphical software.

Summary tables will be based only on all available data. For categorical variables, the numerator, denominator, rate (%), and exact 95% CI will be calculated. For continuous variables, the median, mean, standard deviation, interquartile range, number of observations, minimum and maximum values, and 95% CI, as appropriate, will be presented. For each parameter, the baseline value will be defined as the last non-missing value collected at the time closest to but before treatment with the investigational device.

All statistical tests will be performed at the two-sided 0.05 significance level, unless otherwise specified.

The analyses described in this section assume that 204 subjects have been enrolled and 30-day follow-up complete, and that 72 of those subjects have been consented to the DUS sub-study. If the sub-study has not completed enrollment by the time 204 subjects are enrolled in the main study, the analyses described below, with the exception of the DUS sub-study, will be completed on the full 204 subjects and study results will be declared as planned .This will be considered the primary analysis.

Statistical Analysis Plan 31Mar2023

Enrollment will continue until 72 subjects are consented to the DUS sub-study. Once follow-up in the sub-study is complete, all analyses will be re-run on the full complement of subjects enrolled and that analysis will be considered as a supplemental dataset. This plan ensures the statistical methodology for the primary analysis remains unaltered.

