8.5.2 Secondary Effectiveness Endpoint Analysis

Time to Discharge Eligibility- defined as elapsed time between removal of the final Mid-Bore VVCS device (treatment arm) or removal of the final sheath (control arm) and when the subject is eligible for discharge from the institution based on the assessment of the attending physician. The average time to discharge eligibility will be compared between the treatment and control groups at the 0.025 level of significance. The specific hypotheses being tested are:

Ho: $\mu_{Mynx \ Control} \geq \mu_{manual \ compression}$

Ha: $\mu_{Mynx \ Control} < \mu_{manual \ compression}$

where μ_x is the average time to discharge eligibility for the specified group. A p-value for this one-sided test less than 0.025 will indicate that the time to discharge eligibility for the subjects using the MYNX CONTROLTM Venous VCD was significantly less than for those where manual compression was used. The standard two group T-test will be used to make this comparison.

The difference between average times will also be calculated along with a 95% confidence interval based on the T-distribution.

The remaining secondary endpoint comparisons between MYNX CONTROL™Venous VCD and manual compression are considered ad hoc analyses.

If the distribution assumption of normality the secondary effectiveness endpoint does not hold based on Shapiro-Wilk test at the 0.05 alpha level, a non-parametric Wilcoxon rank sum test will be used to compare the treatment groups.

Procedural Success: attainment of final hemostasis at all venous access sites without major venous access site closure-related complications through 30 days. The proportion of subjects achieving procedural success will be calculated for each treatment group. Those proportions will be compared using both the Pearson Chi-square statistic and Fisher's Exact Test.

Device Success: ability to deploy the VCD delivery system, deliver the polyethylene glycol hydrogel sealant, and achieve hemostasis. This endpoint will be summarized for

the MYNX CONTROL[™] Venous VCD arm only. The proportion of devices that achieve success will be estimated along with a 95% confidence interval calculated using the Clopper-Pearson (exact binomial) method.

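### The device-success interval treats devices in the same subject as independent, and the per-limb minor-complication intervals have no clustering adjustment; reported precision is overstated if within-subject outcomes are correlated

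*SAP*

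**What the plan says.** **Device success.** SAP 8.5.2: "The proportion of devices that achieve success will be estimated along with a 95% confidence interval calculated using the Clopper-Pearson (exact binomial) method". Protocol 16.9.3 takes the access site as the unit: "achieve hemostasis will be summarized on a per access site basis for the device group only". It also lists device success among the secondary endpoints that are ad hoc and not powered. On cluster size, SAP section 5 states: "For the sample size calculation, it is assumed that each subject has 3 access sites in the femoral vein". Protocol 16.8 allows up to four.

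**Minor complications.** SAP 8.4.2: "The proportion of limbs experiencing a minor closure related complication will be calculated for each treatment group along with 95% confidence intervals". On the contrast between arms: "The difference between the proportions will then be estimated along with a 95% confidence interval". Protocol 16.9.2 matches this ("The proportion of limbs experiencing a minor closure related complication will be calculated for each treatment group"). Neither section names an interval method. The general rule in SAP 8.1 is: "For categorical variables, the numerator, denominator, rate (%), and exact 95% CI will be calculated". No method for the difference is named anywhere.

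**Where clustering is handled.** SAP 8.4.1 analyses major complications, on the same limbs, by GEE logistic regression with a compound symmetric working structure. SAP 8.5.1 analyses time to hemostasis, on the same access sites, with subject as a random effect. SAP section 5 calls the within-subject correlation between limbs unknown, and expects bilateral subjects: "To the extent that some subjects will contribute multiple limbs to the actual analysis".

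**The concern.** Clopper-Pearson assumes independent trials. Devices placed in one subject share that subject's anatomy, anticoagulation and operator, so their outcomes may well move together. The plan accepts this for time to hemostasis at the same sites, and hemostasis is one component of device success. It gives no reason for treating the sites as independent here.

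The same gap appears, less sharply, for minor complications. Limbs are clustered for the primary safety endpoint, but no adjustment is given for the secondary one. The per-arm interval falls to an independence-based default, and the interval for the difference is left open.

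At stake is the precision reported for two named secondary endpoints. For device success the interval is all the inference planned, and for minor complications the interval on the difference is the main between-arm statement.

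**Working it through.** **Inputs from the documents.** Arms of 136 and 68 subjects (Protocol synopsis); three access sites per subject for planning (SAP section 5), up to four (Protocol 16.8); one or two limbs per subject.

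**Assumed, because the documents give no values.** ICC from 0 to 0.667; bilateral share of 25%, 50% or 100%; device success rate 0.90 to 0.99; minor-complication rate 0.02 to 0.20; one device per site; beta-binomial clustering; a Wald interval for the difference.

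**The plan's own figures.** For these intervals the plan states only the nominal 95%. At ICC 0, Clopper-Pearson on 136 × 3 = 408 devices covers 96.0% on average, so it meets its level under independence. The nearest stated design figure, about 80% power for primary safety with one limb per subject, also reproduces: Φ(0.05/√(0.015 × 0.985 × (1/68 + 1/136)) − 1.96) = 79.1%.

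**Device success.** Exact coverage of Clopper-Pearson, three devices per subject, averaged over success rates 0.90 to 0.99:

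| ICC | 0 | 0.05 | 0.1 | 0.2 | 0.3 | 0.5 | 0.667 |
|---|---|---|---|---|---|---|---|
| Coverage | 96.0% | 95.0% | 93.9% | 91.8% | 89.6% | 85.2% | 81.8% |

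With four devices per subject and a 95% success rate, coverage is 92.9% at ICC 0.1 and 80.5% at 0.5.

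The design effect is 1 + (3 − 1) × ICC. For 388/408 = 95.1%:
- as planned: 92.5% to 97.0%
- ICC 0.2: design effect 1.4, effective n = 408/1.4 = 291, interval 92.0% to 97.3%
- ICC 0.5: design effect 2.0, effective n = 204, interval 91.2% to 97.6%

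**Minor complications, per arm.** Exact interval, device arm, averaged over rates 0.02 to 0.20:

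| Bilateral share | ICC 0.1 | 0.2 | 0.3 | 0.5 |
|---|---|---|---|---|
| 25% | – | 95.6% | 95.2% | 94.4% |
| 50% | 95.6% | 94.9% | 94.2% | 92.8% |
| 100% | 95.1% | 94.1% | 93.0% | 90.8% |

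In the control arm at 50% bilateral, coverage is 95.5%, 94.8% and 93.5% at ICC 0.2, 0.3 and 0.5.

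At 50% bilateral, the device arm has 68 subjects with one limb and 68 with two, so 204 limbs. The size-weighted mean cluster size is (68 × 1 + 68 × 4)/204 = 1.667, and the design effect at ICC 0.3 is 1 + 0.667 × 0.3 = 1.20. For 20/204 the interval moves from 6.1%–14.7% to 5.8%–15.3%.

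**Minor complications, difference.** With an independent-limb Wald interval, 50% bilateral and a 10% rate in both arms, simulated coverage is 94.7% at ICC 0, 93.1% at 0.2, 92.0% at 0.3 and 90.7% at 0.5. The difference is affected more than the per-arm intervals because the Wald interval lacks the conservatism of the exact one.

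**Do the repairs work?** For device success at rates 0.90 and 0.95, an exact interval on an effective sample size estimated from the between-subject variance covers 95.5% to 96.4% for ICC 0 to 0.667. For the difference, a cluster-robust Wald interval covers 94.1% to 94.8% over all settings run.

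**The case against.** The sponsor can fairly reply that these are descriptive intervals. Trial success (Protocol 16.9.1) depends only on the primary endpoints. Device success is single-arm with no performance goal, and the minor-complication endpoint is summarized without a hypothesis or margin. The absolute shifts in the examples are small. All of this stands, and it limits the weight of the point.

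Four stronger readings might be inferred, and the documents do not support them:

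- **That both intervals necessarily cover less than 95%.** This needs positive correlation, large enough to outweigh the conservatism of the exact interval: above about 0.05 for devices. For limbs, coverage stays at about 95% up to ICC 0.3 with 25% bilateral, 0.2 with 50% and 0.1 with 100%.
- **That the SAP prescribes an independent-limb formula for minor complications.** SAP 8.4.2 names none. The exact per-arm interval is inferred from SAP 8.1, and a single-proportion rule cannot supply an interval for a difference. There the defect is an unstated method.
- **That the ICC for device success is about 0.67, giving 82% coverage.** SAP section 5 puts within-subject variation at about half of between-subject variation, but for time to hemostasis. Even read as a variance ratio, it concerns a continuous outcome on the log scale and does not carry over to binary device success.
- **That this is the only formal comparison of minor complications.** No test is attached, and SAP 8.7 plans further minor-complication analyses by number of sites, sheath size and number of limbs.

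What survives is that the SAP names an independence formula for clustered devices, and leaves clustering unaddressed for minor complications while modelling it for major ones.

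**Conclusion.** The point holds in conditional form, with device success as the lead item. Followed as written, SAP 8.5.2 gives an interval that under-covers once the ICC exceeds about 0.05: about 94% at 0.1, 92% at 0.2 and 85% at 0.5, for 136 subjects with three devices each. For minor complications the per-arm loss is small: device-arm coverage is about 95%, 94% and 93% at ICC 0.2, 0.3 and 0.5 with half of subjects bilateral, with no shortfall at low ICC or low bilateral share. The difference could lose more (92.0% at ICC 0.3), but only if an independent-limb Wald interval were chosen. The results rest on the assumed ICC, bilateral share, event rates and beta-binomial model. No primary conclusion changes; a wording change before analysis is justified because the gap is clear and cheap to close.

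**What to change.** 1. **Device success (SAP 8.5.2).** Replace the device-level Clopper-Pearson interval with an exact interval on an effective sample size: devices divided by the estimated design effect, never more than the device count. State the rule when every device succeeds, because the design effect cannot then be estimated. Counting devices gives a lower bound of 0.025^(1/408) = 99.1%; counting subjects, which is conservative, gives 0.025^(1/136) = 97.3%. A plain robust-variance or subject-bootstrap interval is not enough, since it has zero width in that case. Use one unit, device or access site, in both documents.
2. **Minor complications (SAP 8.4.2, Protocol 16.9.2).** Use the GEE already specified for primary safety, clustered on subject with robust variance, for the per-arm proportions and for their difference. Name a fallback if an arm has no events.

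The cost is SAP text, matching wording in the protocol and somewhat wider intervals: about √1.4 − 1 = 18% for devices at ICC 0.2, and √1.2 − 1 = 10% for limbs at 50% bilateral and ICC 0.3. No further subjects or data are needed.

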8.4.3 Additional Safety Analysis

The type of major complication will also be compared on a per-limb basis. Frequency distributions for the type of complication will be constructed for each treatment group and the frequency distributions will be examined informally. This analysis is for information purposes only.

8.5 Analyses of Effectiveness Endpoints

8.5.1 Primary Effectiveness Endpoint Analysis

There are two co-primary effectiveness endpoints: Time to hemostasis, and time to ambulation.

The average time to ambulation in each treatment group will be compared using a standard T-test. The test will be done on a per subject basis. The null and alternative hypotheses are:

Ho: $\mu_{Mynx \ Control} \geq \mu_{manual \ compression}$

Ha: $\mu_{Mynx \ Control} < \mu_{manual \ compression}$

where μ_x is the average time to ambulation for the specified group. A p-value for this one-sided test less than 0.025 will indicate that the time to ambulation for the subjects using the MYNX CONTROLTM Venous VCD was significantly less than for those where manual compression was used.

The average time to hemostasis will be analyzed on an access site level. The null and alternative hypotheses of the primary effectiveness comparison for TTH are given below:

Ho: $\mu_{manual \ compression} - \mu_{Mynx \ Control} \le 5$ Ha: $\mu_{manual \ compression} - \mu_{Mynx \ Control} > 5$

where μ_x is the mean time to hemostasis for the indicated group and 5 minutes is superiority margin.

The average time to hemostasis will be analyzed using a generalized linear mixed model where subject is considered a random effect with multiple access sites and treatment group is a fixed effect. The times to hemostasis in the manual compression group will be reduced by 5 minutes to account for the hypothesis that the time to hemostasis for the MYNX CONTROL[™] Venous VCD device is at least 5 minutes less than manual compression. The analysis will consist of testing the coefficient on the fixed effect for treatment group. If that coefficient is found to be significantly different from zero, then the direction will be evaluated to assure that the hemostasis time is reduced on average when using MYNX CONTROL[™] Venous VCD. This test is by default a two-sided test, so a p-value of 0.05 or less with the direction of the difference showing shorter times for MYNX

CONTROL[™] Venous VCD will correspond to a one-sided test at the 0.025 level results in achieving this endpoint.

If the distribution assumptions (normality, lognormality) for the primary effectiveness endpoints do not hold based on Shapiro-Wilk test at the 0.05 alpha level, a non-parametric Wilcoxon rank sum test will be used to compare the treatment groups.

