14.1 Index Procedure

The Instructions for Use (IFU) provides detailed information on the product, safety, storage, design, deliverability, and sizing specifications. All information within the IFU should be referenced prior to each procedure and implantation of the study device.

If a subject is randomized to receive manual compression, it should be performed according to the institution's standard of care practice. If protamine is administered, the Investigator should follow institutional practice guidelines for re-checking ACT levels and/or waiting a specified time or for a target ACT value prior to removal of sheaths and application of manual compression.

If a subject is on Warfarin, any pre-procedure standard of care requirements should be followed.

The following will be collected at the time of the procedure:

- **A0:** Time of first index procedure sheath insertion
- A1 Time: time of removal of final index procedure device
- Sheath sizes used during procedure
- For each access site, the following should be recorded:
 - Access site location (left/right leg and location with respect to 2nd access site, if applicable)
 - **HX.1 Time:** time of removal of MYNX CONTROL[™] Venous device (device group) or removal of sheath (control group)

Version: 3.0 / 31Jan2023

- o HX.2 Time: time venous hemostasis is achieved.
- Confirm venous hemostasis is maintained at 5 min after recorded hemostasis time (HX.2)
- Use of adjunctive compression (e.g., light manual compression, sandbags, or mechanical compression devices)

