16.1 Randomization

This is a randomized, controlled, open label study. Before the first subject is enrolled in the study, a randomization schedule will be generated by the study statistician and uploaded into an electronic database that can be accessed via computer. The schedule will be generated using a

Version: 3.0 / 31Jan2023

permuted block approach. Randomization will be performed at the conclusion of the index procedure, while the patient is on the table and the operator is able to visualize all access sites to verify eligibility. Since one of the primary endpoints of this study is time to ambulation, randomization will be done at the patient level to avoid the possibility of a patient receiving both MYNX CONTROL[™] Venous VCD and manual compression. Randomization will be stratified by study center with a 2:1 randomization ratio for MYNX CONTROL[™] Venous VCD vs. manual compression for access site closure. Roll-in patients will not be randomized. All roll-in patients will receive the MYNX CONTROL[™] Venous VCD.

Any physician delegated as "Operator" on the Delegation of Authority log needs to have two (2) roll-in patients prior to randomizing any subject.

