16.10 Sub-Group Analysis

A sub-group analysis will be completed for the primary safety and primary efficacy endpoints. This analysis is not powered and is strictly for information purposes. The sub-groups for this analysis are those subjects that contributed only 1 limb and those subjects that contributed 2 limbs. The same analysis outlined above for the primary safety and efficacy endpoints will be completed within each sub-group separately. Additional analyses to demonstrate the homogeneity of the treatment effect and homogeneity of the major complication rates are detailed in the SAP.

Major and minor complications will also be analyzed based on the number of access sites and sheath size, major and minor complications will be stratified by number of access sites per leg (1, 2, 3, or 4 sites), total number of access sites per patient (1, 2, 3, or 4 sites), and sheath size (small size vs. large size). Details are provided in the SAP.

A sub-group analysis will also be performed utilizing independent analysis of non-invasive duplex ultrasound (DUS) imaging in 72 subjects from both arms (48 device and 24 control) at the time of the procedure, pre-discharge and potentially again at the 30-day follow-up (only for those subjects that have documented evidence of access site complications at the discharge ultrasound). Specific investigational sites will be designated as ultrasound sites. These sites will include subjects in the ultrasound subset imaging until a total of 72 patients have been evaluated in both treatment arms. Ultrasound will be performed at the follow-up office visit only if a complication was detected at discharge. All sub-study sites will be instructed in performance of duplex ultrasonography of the femoral vascular structures. Images will be interpreted by:

NAMSA [name]

Version: 3.0 / 31Jan2023

[name]

At the time of the procedure, and at discharge, the proportion of subjects exhibiting a complication on DUS imaging will be calculated along with 95% confidence intervals constructed using the Clopper-Pearson method. For those subjects that required a DUS at the 30 day follow-up, the proportion of subjects still exhibiting a complication will be calculated along with a 95% confidence interval constructed using the Clopper-Pearson method.

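### Access-site count, number of limbs, sheath size and center are known before randomization but enter neither co-primary analysis: the tests are valid, but precision of unknown size is forgone, mainly for time to ambulation

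*SAP*

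**What the plan says.** SAP 8.5.1 gives the TTA analysis in one sentence: "The average time to ambulation in each treatment group will be compared using a standard T-test". The TTH analysis in the same section is a mixed model with subject as a random effect and treatment as the only fixed effect. If a Shapiro-Wilk test at 0.05 rejects the distributional assumption for either endpoint, a Wilcoxon rank sum test takes over. It carries no covariates either.

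Protocol 16.1 places randomization at the end of the index procedure, "while the patient is on the table and the operator is able to visualize all access sites to verify eligibility". Protocol 13.2 adds that all procedural sheaths are in place by then. Protocol 14.1 records the sheath sizes used and, for each site, "Access site location (left/right leg and location with respect to 2nd access site, if applicable".

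The plan regards these factors as relevant. Protocol 16.10 breaks complications down by "total number of access sites per patient (1, 2, 3, or 4 sites), and sheath size", among others. SAP 8.7 lists site count, sites per limb, sheath size and number of limbs as sub-groups for the primary endpoints, in unpowered models meant for information.

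Randomization is stratified by center alone (Protocol 16.1, SAP 7). Center then appears only in the poolability models of SAP 9.

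**The concern.** The three access factors cannot be affected by treatment, so adjusting for them is safe. A link to TTA is plausible from the endpoint itself: the subject must walk without rebleeding from any femoral venous site, and a subject with four sites has more ways to be held back than a subject with one. Center is also plausible, because Protocol 14.2 leaves control-arm ambulation to institutional guidelines.

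Whatever these variables explain now sits in the error term. Protocol 16.9.1 requires both efficacy endpoints and the safety endpoint for trial success, so a missed TTA test fails the trial. The trial is also open label. If the arms turn out visibly different in bilateral access or sheath size, an adjusted estimate will be asked for, and under the present SAP it would be post hoc.

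**Working it through.** **Inputs from SAP 5.** Error rate: "The Type 1 error for this calculation was set at 0.025 for a one-sided test". Mean TTA: 3.0 h with the device against 6.0 h with manual compression, a difference of 3 h. Spread: "both groups have a standard deviation of 6.0 hours". Stated result: 192 evaluable subjects for 90% power. Allocation is 2:1, and 5% missing data is allowed for.

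**The plan's own figure.** Controls needed = (1 + 1/2) × (1.960 + 1.282)² × (6/3)² = 63.04, rounded up to 64. With 128 device subjects the total is 192, as stated. 192/0.95 = 202.1, so 203, and 204 for a 2:1 split. The standard error (SE) of the difference is 6 × √(1/128 + 1/64) = 0.919 h. The noncentrality is 3/0.919 = 3.27, and the noncentral t power is 90.1%.

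**Effect of adjustment on TTA.** Let R² be the share of TTA variance that the covariates explain. The documents give no value; 0.05 to 0.30 is an assumption. The residual SD is 6 × √(1 − R²). The part of the estimated difference that comes from chance covariate imbalance has SD 0.919 × √R².

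| R² (assumed) | Residual SD (h) | Power at 128/64 | N for 90% power | SD of imbalance part (h) |
|---|---|---|---|---|
| 0 | 6.00 | 90.1% | 192 | 0 |
| 0.05 | 5.85 | 91.5% | 180 | 0.21 |
| 0.10 | 5.69 | 92.9% | 171 | 0.29 |
| 0.20 | 5.37 | 95.3% | 153 | 0.41 |
| 0.30 | 5.02 | 97.3% | 135 | 0.50 |

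If the true difference were 2.5 h, power would go from 77.3% unadjusted to 81.4%, 85.7% and 89.9% at R² of 0.10, 0.20 and 0.30.

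**Simulation check.** 20,000 normal-data trials per setting, 64 against 128, one covariate. One-sided type I error was 0.023 to 0.026 with and without adjustment. Adjusted power was 92.4%, 95.1% and 97.3% at R² of 0.10, 0.20 and 0.30. At R² = 0 it was 89.8%, against 89.9% for the t-test.

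**Chance imbalance.** For a factor present in half of subjects (assumed), the SD of the difference in proportions is √(0.25 × (1/136 + 1/68)) = 7.4 points. The chance of a gap of at least 10 points is 2 × (1 − Φ(10/7.43)), about 18%. In hours, 95% of trials have an imbalance part within ±1.96 × 0.21 = ±0.4 h (R² = 0.05) to ±1.96 × 0.50 = ±1.0 h (R² = 0.30), against a planned 3 h effect.

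**TTH.** The log-scale SD is not given, so the stated power cannot be rebuilt. It can be taken as given: 95% at 100/50 implies difference/SE = 1.645 + 1.960 = 3.605. At 128/64 this becomes 3.605 × √(192/150) = 4.08, a power of 98.3% unadjusted. I use three sites per subject and read within-subject variance as half of the between-subject variance. Covariates explaining a share R² of between-subject variance then multiply the variance by (1 − R² + 0.5/3)/(1 + 0.5/3). That gives 98.9% at R² = 0.10 and 99.7% at 0.30.

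**Which TTA test would be used.** TTA cannot be negative. A normal distribution with mean 3 and SD 6 would put Φ(−3/6), about 31%, of device subjects below zero. Under the plan's own mean and SD, every simulated lognormal sample failed Shapiro-Wilk at 0.05. The Wilcoxon test would then decide TTA, and an adjusted linear model written into the SAP with nothing else changed would go unused.

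**The case against.** The strongest reply is that nothing is wrong. An unadjusted comparison in a randomized trial is valid, and the plan's 192 and 204 reproduce with exactly that test. A reader might infer that the plan is biased by imbalance, that its type I error is off, or that it demonstrably wastes power. The documents support none of these. Chance imbalance is random error already counted in the standard error, and no section says how strongly the factors predict either time.

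There are also reasons to expect a weak link with TTA. Protocol 14.2 sets a 2 to 2.5 hour window for the device-arm attempt. Pre-procedural exclusion 15 removes patients whose ambulation is expected to be late. The TTA clock starts at final removal, so extra sites do not mechanically add closure time. Power may also be higher than planned: the SDs cited for time to discharge eligibility are 1.3 and 1.9 h. If the TTA SD were near 2 h, the noncentrality would be 3/(2 × 0.153) = 9.8 and power practically 100% without adjustment. SAP 8.7 would also expose any dependence on these factors.

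All of this bears on the size of the gain, and it stands: the gain may be small. It does not show that adjustment would do harm. The SAP 8.7 models are informational and test interactions, so they do not supply a pre-specified adjusted treatment effect.

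Four practical objections also stand, and the fix has to meet them. The Wilcoxon fallback would discard the adjustment. Center has at least as good a documentary case as the access factors. Protocol 14.1 lists sheath size at procedure level, not per site. Limb and site counts overlap, since two limbs imply at least two sites.

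**Conclusion.** The point holds as a missed precision gain of unknown size, mainly for TTA. It is an improvement worth making, not an error to correct. The planned tests are valid and deliver the stated 90% TTA power.

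The range of 91.5% to 97.3% rests wholly on an assumed R² of 0.05 to 0.30, on the plan's 3 h difference and 6 h SD, and on normal-theory tests. At R² = 0 there is no gain. For TTH the gain is about one point, given the stated 95% power at 150 subjects. The 18% chance of a 10-point imbalance assumes a factor with 50% prevalence and describes random error, not bias. The firmest reason to act is pre-specification: the data exist, they precede randomization, and the adjusted estimate is likely to be wanted.

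**What to change.** In SAP 8.5.1 and Protocol 16.9.1:

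- **TTA:** use a linear model with treatment, center (small centers pooled by a rule stated in advance), number of access sites, number of limbs (1 or 2) and largest sheath size. Test the treatment coefficient at one-sided 0.025.
- **TTH:** add the same subject-level fixed effects to the mixed model. Largest sheath per subject fits the way sheath size is listed in Protocol 14.1, so no link from sheath to site is needed.
- **Distribution check:** state that Shapiro-Wilk applies to model residuals.
- **Fallback:** replace the unadjusted Wilcoxon test with a covariate-adjusted method, for example rank-based ANCOVA or robust standard errors. Robust standard errors keep the hypothesis on means. For TTH the method should also respect clustering of sites within subject.
- **Sensitivity:** keep the unadjusted analyses.

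The cost is a few extra parameters and a minor text amendment to both documents; for the protocol this goes through the amendment process in Protocol 17.5.1. No new data are needed. If the covariates predict nothing, the simulated loss with one covariate was about 0.1 point of power.
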